9.2 Handling of Missing Data

Missing data could occur due to various reasons, including missing visits/assessments, early withdrawal from the study, or missing due to COVID-19 infection or logistic restriction.

The COVID-19 pandemic is interfering with the conduct of many ongoing trials, with potential impacts on treatment duration and the collection, analysis and the interpretation of clinical trial data. Some protocol-specified visits in the clinical trials may be impacted due to COVID-19 infection or logistical restrictions during the pandemic. For example, some scheduled visits may be missed due to self-quarantine or local government restrictions on travel; some visits may also be delayed or canceled due to healthcare resource constraints during the pandemic. Impacted visits due to COVID-19 will be recorded in the database. The probability of having missed visits and missing data due to COVID-19 infection or logistical restrictions related to the COVID-19 pandemic can be reasonably assumed to be unrelated to the unobserved values. Therefore, for the purpose of statistical analysis, it is reasonable to assume that these missing data are missing at random (MAR) and the statistical models that require MAR assumption are appropriate. Sensitivity analyses will be performed to assess the impact of missing data and the robustness of the conclusion.

Handling of missing data for the efficacy analyses is described below.

9.2.1 Categorical Endpoints

Non-Responder Imputation incorporating multiple imputation to handle missing data due to COVID-19 (NRI-MI) will be the approach for handling missing data in the analysis of categorical endpoints among all ITT Populations except for the ITT_Res Population. The NRI-MI will categorize any subject who does not have an evaluation during a pre-specified visit window as a non-responder for the visit. The only exceptions are: 1) when the subject is a responder both before and after the visit window in the particular Study Period, the subject will be categorized as a responder for the visit; 2) missing data due to COVID-19 infection or logistical restriction will be handled by MI. Subjects who receive alternative PsO treatment regardless of premature discontinuation of study drug or receive RZB as the rescue medication will be counted as non-responders at later visits. Subjects whose change/percent change from Baseline cannot be calculated because of a missing Baseline will be considered as a non-responder at all post-baseline visits, unless the post-baseline value is zero. More details are provided in [Appendix D](#).

Of note, during the Primary Analysis for Period A upon completion of Week 16, the NRI-MI analysis will only be performed at all visits up to Week 16.

Observed Cases (OC) will be the approach for handling missing data in the analysis of categorical endpoints among the ITT_Res Population. The OC analysis will not impute values for missing evaluations, and thus a subject who does not have an evaluation on a scheduled visit will be excluded from the OC analysis for that visit. OC will exclude values after a subject receive alternative PsO treatment regardless of premature discontinuation of study drug.

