### Summary and Analysis of Additional Efficacy Endpoints

Additional binary endpoints will be analyzed among each Population as follows:

- Comparison of additional endpoints among the ITT\_A and ITT\_LT Populations will be made using CMH test adjusting for the actual values of stratification factors in the initial randomization at Baseline. NRI-MI will be used to handle missing data.
- Comparison of additional endpoints among the ITT\_B\_NR Population will be made using Chi-square test. NRI-MI will be used to handle missing data.
- Comparison of additional endpoints among the ITT\_B\_Combined Population will be made using CMH test adjusting for the actual value of the stratification factor in the re-randomization at Week 16. NRI-MI will be used to handle missing data.
- Summary statistics will be provided for additional endpoints among the ITT\_B\_R Population. NRI-MI will be used to handle missing data.
- Summary statistics will be provided for additional endpoints among the ITT\_Res Population, based on Observed Cases (OC).

Additional continuous endpoints will be analyzed among each Population as follows:

- Comparison of additional endpoints on ITT\_A and ITT\_LT Population will be made based on the fixed term of treatment from a Mixed-effect Model Repeat Measurement (MMRM), adjusting for treatment, actual values of stratification factors and Baseline value if applicable (if not duplicating the stratification factors).
- Comparison of additional endpoints on ITT\_B\_NR Population will be made based on the fixed term of treatment from a MMRM, adjusting for treatment and Baseline value.
- Comparison of additional endpoints among the ITT\_B\_Combined Population will be made based on the fixed term of treatment from a MMRM, adjusting for treatment, actual values of stratification factors in the re-randomization at Week 16 and Baseline value.
- Summary statistics will be provided for additional endpoints among the ITT\_B\_R Population, based on the fixed term of treatment from a MMRM, adjusting for treatment and Baseline value.

- Summary statistics will be provided for additional endpoints among the ITT\_Res Population, based on OCs.

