4.0 Analysis Populations

The following analysis populations will be used for the analyses.

The Intent to Treat Population in Period A (ITT_A) includes all randomized subjects. The ITT_A Population will be used for all efficacy analyses in Period A.

The Intent to Treat Population for APR-PASI75NRs in Period B (ITT_B_NR) includes subjects randomized at Baseline (Day 1), fail to achieve PASI 75 at Week 16 and are re-randomized. The ITT_B_NR Population will be used for the analysis comparing switch-to-RZB (APR/RZB) vs. continue-with-APR (APR/APR) among APR-PASI75NRs in Period B.

The Intent to Treat Population for APR-PASI75 responders in Period B (ITT_B_R) includes subjects randomized to APR at baseline, achieve PASI 75 at Week 16 and are re-randomized (APR-PASI75Rs). The ITT_B_R Population will be used for the summary of efficacy for APR/RZB and APR/APR among APR-PASI75Rs in Period B.

The Intent to Treat Population for Period B combined Population (ITT_B_Combined) includes subjects randomized to APR at Baseline and are re-randomized at Week 16. The ITT_B_Combined Population will be used for combined analysis (APR-PASI75NRs and APR-PASI75Rs) between subjects re-randomized to APR/RZB and APR/APR in Period B.

The Intent to Treat Population for Long Term Efficacy (ITT_LT) includes subjects randomized to receive continuous RZB (i.e., all subjects randomized to RZB at Baseline) and subjects randomized and re-randomized to receive continuous APR, including half of the subjects randomized to APR at Baseline and prematurely discontinued from study before entering Period B. The ITT_LT Population will be used for the analysis comparing long term efficacy between continuous treatment of RZB/RZB and APR/APR in Period B. Of note, the algorithm to select half of the subjects randomized to APR at Baseline and prematurely discontinued from study before entering Period B is defined as follow:

1. Rank all such subjects by their subject ID in ascending order (as 1, 2, 3...).
2. Select subjects whose ranks are even numbers.

The Intent to Treat Population for Rescued Population (ITT_Res) includes subjects who are re-randomized to APR at Week 16, fail to achieve PASI 50 at Week 28 and/or Week 40, and receive RZB as the rescue medication. The ITT_Res Population will be used for the summary of efficacy after being rescued with RZB.

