9.5 Additional Efficacy Analyses

All additional efficacy endpoints will be analyzed as specified in Section 9.1.

Period A: Additional efficacy endpoints will be compared between the RZB and APR treatment groups among the ITT_A Population at each visit.

Period B: Additional efficacy endpoints will be compared between the APR/RZB and APR/APR treatment groups among the ITT_B_NR and ITT_B_Combined Populations, and between the RZB/RZB and APR/APR treatment groups among the ITT_LT Population, at each visit in Period B.

Additional efficacy endpoints will also be summarized by the APR/RZB and APR/APR treatment groups among the ITT_B_R Population at each visit in Period B.

During the Period of Rescue RZB: Additional efficacy endpoints will be summarized among the ITT_Res Population at each visit after the use of Rescue RZB.

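### Categorical response after rescue risankizumab (ITT_Res) is planned on observed cases only; a non-responder summary of all rescued subjects should stand beside it

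*SAP*

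**What the plan says.** SAP 4.0 defines ITT_Res as subjects re-randomized to apremilast at Week 16 who "fail to achieve PASI 50 at Week 28 and/or Week 40, and receive RZB as the rescue medication". SAP 9.5 gives the use of this population: "Additional efficacy endpoints will be summarized among the ITT_Res Population at each visit after the use of Rescue RZB". No comparison or test is attached to it.

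For categorical endpoints SAP 9.2.1 applies NRI-MI to all the other ITT populations and then makes one exception: "Observed Cases (OC) will be the approach for handling missing data in the analysis of categorical endpoints among the ITT_Res Population". Two consequences are spelled out there:

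- Missing evaluation: "thus a subject who does not have an evaluation on a scheduled visit will be excluded from the OC analysis for that visit".
- Alternative psoriasis treatment: "OC will exclude values after a subject receive alternative PsO treatment regardless of premature discontinuation of study drug".

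Protocol 7.4, under the additional efficacy endpoints, also bases the ITT_Res summary of binary endpoints on observed cases.

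The rule for the other populations is in the same SAP section: "The NRI-MI will categorize any subject who does not have an evaluation during a pre-specified visit window as a non-responder for the visit". Subjects who take alternative psoriasis treatment or receive rescue risankizumab "will be counted as non-responders at later visits". There are two exceptions. A subject who responds both before and after the missed window is a responder, and COVID-19 losses are multiply imputed.

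Neither document gives a reason for treating ITT_Res differently, plans a non-responder version for it, or states its expected size or loss.

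**The concern.** The same event is scored in opposite ways. Elsewhere in the plan, moving to another psoriasis treatment is a failure; after rescue it takes the subject out of the rate from then on. A rescued subject who does not respond and moves on therefore raises the reported percentage. The population carries an intent-to-treat label, but the percentage and its 95% confidence interval (SAP 9.1) describe only those still observed without other treatment.

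ITT_Res is the plan's dedicated summary of efficacy after rescue. Readers may set it beside the APR/RZB rates, because both groups began on apremilast and later received risankizumab. The two rates would rest on different failure rules, and nothing in the planned output would show how much of any similarity or difference comes from that.

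**Working it through.** **Inputs.** The scoring rules come from SAP 9.2.1, membership from SAP 4.0, and the reported output (number, proportion, 95% CI) from SAP 9.1. The documents give no figure for ITT_Res to reproduce. The sample-size figures in SAP 2.4 concern the Period A co-primary and Period B primary comparisons and do not enter here.

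**Formulas.** At a given visit let N be the subjects rescued by then, k those excluded under OC, and r the responders among the N - k observed.

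- OC rate = r/(N - k)
- Non-responder rate = r/N
- Ratio = 1/(1 - k/N)
- With p = r/N and f = k/N, gap = p x f/(1 - f)

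Whenever r and k are both at least 1, the OC rate is the higher. With k = 0 the two are equal.

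**Illustration (assumed values, none from the documents).** With N = 30, r = 18 and k = 3, the non-responder rate is 18/30 = 60.0% and the OC rate is 18/27 = 66.7%.

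| Excluded (f) | Ratio | OC rate if non-responder rate is 60% | Gap in points, for p from 40% to 60% |
|---|---|---|---|
| 0% | 1.00 | 60.0% | 0 |
| 5% | 1.05 | 0.60/0.95 = 63.2% | 2.1 to 3.2 |
| 10% | 1.11 | 0.60/0.90 = 66.7% | 4.4 to 6.7 |
| 15% | 1.18 | 0.60/0.85 = 70.6% | 7.1 to 10.6 |
| 20% | 1.25 | 0.60/0.80 = 75.0% | 10.0 to 15.0 |

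**Where the direction is not fixed.** The ratio assumes that each excluded subject would be scored a non-responder. For an intermittent missed visit the before-and-after exception can reverse it. Suppose 2 of 40 subjects miss a visit but respond on both sides of it, and 20 of the 38 observed respond. OC gives 20/38 = 52.6%, and the non-responder rule gives 22/40 = 55.0%. This cannot happen for subjects who have left, or at Week 52, the last efficacy visit. COVID-19 losses also fall outside the ratio, since the other populations impute them.

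**Against true response.** If excluded subjects respond at rate q, the rate among all N is (r + qk)/N. OC exceeds this only if q < r/(N - k). In the example, q = 2/3 gives (18 + 2)/30 = 66.7%, equal to OC. The documents contain nothing that fixes q.

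**The case against.** The strongest reply is that OC is a prespecified choice, stated alike in Protocol and SAP, for a descriptive summary outside the testing hierarchy. For the Period B primary and ranked endpoints, subjects who meet the rescue criteria or are rescued already count as non-responders (SAP 8.0). The NRI-MI rule could not be applied to ITT_Res unchanged either: it makes everyone who receives rescue a non-responder afterwards, so every member would fail. All of this stands. It is why the point is a modest addition and does not threaten any conclusion.

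Several stronger readings are tempting, and the documents do not support them:

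- *A reader might infer that the rescue rate is inflated as a matter of fact.* The arithmetic shows only that OC exceeds the plan's own non-responder rate. That rate is a conservative convention, not the truth.
- *A reader might infer that late rescue will look better than immediate switching.* No such comparison is planned. The groups also differ in selection (PASI 50 failure) and in time on risankizumab by Week 52: 24 or 12 weeks after rescue at Week 28 or 40, against 36 weeks after the Week 16 switch. A common missing-data rule would not make them comparable.
- *A reader might infer that subjects are removed altogether.* OC drops only the affected visits, so earlier post-rescue results stay in. Under Protocol 5.6, subjects who stop study drug should continue their visits. Those who do remain in the denominator unless they start other treatment.

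It is also fair that losses have little time to build up, and that in the example the Wilson 95% CI for 18/27, about 48% to 81%, dwarfs the 6.7-point gap. Since SAP 9.1 reports the number of responders and SAP 7.1 describes ITT_Res at Baseline, a reader could form r/N at Week 52. The reasons for exclusion would still be missing, because SAP 5.0 plans no separate disposition summary for rescued subjects.

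**Conclusion.** The point holds as a low-cost improvement. Categorical response in ITT_Res rests on OC alone, although the same events are non-response elsewhere in the plan. For subjects who leave or start alternative psoriasis treatment, and at Week 52 for any loss not due to COVID-19, OC exceeds the non-responder rate by 1/(1 - k/N). Assuming 5% to 15% excluded and a 60% non-responder rate, that is about 3 to 11 points. The size cannot be derived from the documents and is zero if nobody is excluded. An upward bias against true response needs excluded subjects to respond less often than those observed, which is plausible but not shown. No primary or ranked secondary result, alpha or power is affected.

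**What to change.** In SAP 9.2.1 and Protocol 7.4, add for categorical endpoints in ITT_Res:

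1. A non-responder summary with all subjects rescued by that visit in the denominator. A subject is a non-responder if missing for reasons other than COVID-19 or after alternative psoriasis treatment. The clause that makes receipt of rescue itself a non-response must not apply here. The before-and-after exception should use post-rescue visits only, since the Study Period as a whole also covers visits on apremilast.
2. A statement on COVID-19 losses: multiple imputation as elsewhere or, if that is impractical in a small group, plain non-responder imputation labelled as differing from the other populations.
3. The OC summary kept beside it, labelled as conditional on remaining under observation without alternative treatment, with the number excluded by reason at each visit.

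The data are already collected. The cost is a short text change, one more table and a slightly lower reported rescue rate.

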9.2.2 Continuous Endpoints

Mixed-Effect Model Repeat Measurement (MMRM) will be the primary and only approach to handle missing data for continuous endpoints among all ITT Populations except for the ITT_Res Population. The MMRM will be conducted using mixed model including observed measurements at all visits, using all available data even if a subject has missing data at some (but not all) post-baseline visits during the analysis period. Subjects' observations after the use of alternative PsO treatment regardless of premature discontinuation of study drug or after the use of RZB as the rescue medication will be excluded from the model. An unstructured variance covariance matrix (UN) will be used. If the model cannot converge, an appropriate covariance structure matrix (e.g., autoregressive (1) or compound symmetry) will be used. The parameter estimations are based on the method of restrictive maximum likelihood (REML). The fixed effects will be used to report model-based means at corresponding visits.

- Comparison of additional endpoints among the ITT_A and ITT_LT Populations will be made adjusting for treatment, visit and treatment-by-visit interaction, actual values of stratification factors at Baseline, and baseline value (if not duplicating the stratification factors).
- Comparison of additional endpoints among the ITT_B_NR Population will be made adjusting for treatment, visit and treatment-by-visit interaction and baseline value.

- Comparison of additional endpoints among the ITT_B_Combined Population will be made adjusting for treatment, visit and treatment-by-visit interaction, actual values of stratification factors at re-randomization, and baseline value (if not duplicating the stratification factors).
- Summary statistics will be provided for additional endpoints among the ITT_B_R Population, adjusting for treatment, visit and treatment-by-visit interaction and baseline value.

Of note, during the Primary Analysis for Period A upon completion of Week 16, the MMRM analysis will only be performed at all visits up to Week 16.

Observed Cases (OC) will be the approach for handling missing data in the analysis of continuous endpoints among the ITT_Res Population: The OC analysis will not impute values for missing evaluations, and thus a subject who does not have an evaluation on a scheduled visit will be excluded from the OC analysis for that visit. OC will exclude values after a subject receive alternative PsO treatment regardless of premature discontinuation of study drug.

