2.3 Treatment Assignment and Blinding

All subjects will be assigned a unique identification number by the IRT at the screening visit. For subjects who rescreen, the screening number assigned by the IRT at the initial screening visit should be used. The IRT will assign a randomization number that will encode the subject's treatment group assignment according to the randomization schedule.

In Period A (Baseline to Week 16), subjects will be centrally randomized to risankizumab (Arm 1) or apremilast (Arm 2) in a 1:2 ratio at Baseline. Randomization will be stratified

by Baseline body weight (≤ 100 kg, > 100 kg) and prior exposure to any systemic and/or biologic treatment for Po ($0, \geq 1$).

In Period B (Week 16 to Week 52), subjects initially randomized to risankizumab (Arm 1) will continue to receive risankizumab. Subjects initially randomized to apremilast (Arm 2) will be centrally re-randomized at the Week 16 visit in a 1:1 ratio to receive either risankizumab (Arm 2a) or apremilast (Arm 2b). Re-randomization will be stratified by PASI 75 response (responder, non-responder) at Week 16. Rescue risankizumab will be offered to subjects who are re-randomized to apremilast (Arm 2b) and are PASI 50 non-responders at Week 28 (Arm 3a) or Week 40 (Arm 3b).

This is an open-label study; however, the efficacy assessor will remain blinded to each subject's treatment, clinical laboratory results, and all subject safety data during the course of the study.

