3.3 Other Efficacy Endpoints

All variables listed in Section 3.1 and Section 3.2 as primary or ranked secondary endpoints will also be analyzed at all other visits collected. Additionally, the following endpoints will be evaluated at all visits collected:

- Achievement of 100% reduction from Baseline in PASI (PASI 100)
- Achievement of sPGA 0
- Change from Baseline in PASI
- Percent change from Baseline in PASI
- Change from Baseline in body surface area (BSA)
- Achievement of Palmoplantar Investigator's Global Assessment (ppIGA) 0 or 1, among subjects with Baseline ppIGA of at least 3
- Change from Baseline in Psoriasis Scalp Severity Index (PSSI), among subjects with Baseline scores > 0
- Change from Baseline in Nail Psoriasis Severity Index (NAPSI), among subjects with Baseline scores > 0
- Change from Baseline in Dermatology Life Quality Index (DLQI)
- Achievement of DLQI 0 or 1
- Achievement of DLQI improvement (reduction) of ≥ 4 points, among subjects with Baseline DLQI ≥ 4
- Change from Baseline in Work Productivity and Activity Impairment (WPAI) scores
- Treatment Satisfaction Questionnaire for Medication version 9 (TSQM-9) scores (at each post-Baseline visit in Period A)
- Change from Entry of Period B in TSQM-9 scores, among subjects who are re-randomized at Week 16
- Change from Baseline in Psoriasis Symptoms Scale (PSS) scores
- Percentage change from Baseline in PSS, among subjects with baseline scores > 0
- Achievement of PSS 0

- Achievement of PSS 0 or 1

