- ITT_LT Population: Comparisons in Period B will be made between RZB/RZB and APR/APR using the Cochran-Mantel-Haenszel (CMH) test, adjusting for the actual values of stratification factors at Baseline: Baseline body weight (≤ 100 kg, > 100 kg) and prior exposure to any systemic and/or biologic treatment for psoriasis ($0, \geq 1$). In case of any stratum with zero subject in either treatment group, no stratification factor will be controlled.

Continuous Endpoints:

For continuous endpoints, the Baseline mean, visit mean, as well as the Least Square (LS) mean, 95% confidence interval (CI) and Standard Error (SE) of that mean, will be provided by each treatment group among all ITT Populations.

In addition, comparisons between treatment groups will be made in the following analyses, with the estimated treatment difference, as well as the corresponding 95% CI, SE and the p-value will be provided among the following populations:

- ITT_A Population: Comparisons in Period A will be made between RZB and APR based on the fixed term of treatment from a Mixed-effect Model Repeat Measurement (MMRM) model including the Baseline value and observed measurements at all post-baseline visits, adjusting for the fixed effects of treatment, actual values of stratification factors at Baseline, visit and treatment-by-visit interaction as covariates.
- ITT_B_NR Population: Comparisons in Period B comparisons will be made between APR/RZB and APR/APR based on the fixed term of treatment from a Mixed-effect Model Repeat Measurement (MMRM) model including the Baseline value and observed measurements at all post-baseline visits after Entry of Period B, adjusting for the fixed effects of treatment, visit and treatment-by-visit interaction as covariates.

- ITT_Combined Population: Comparisons in Period B comparisons will be made between APR/RZB and APR/APR based on the fixed term of treatment from a Mixed-effect Model Repeat Measurement (MMRM) model including the Baseline value and observed measurements at all post-baseline visits after Entry of Period B, adjusting for the fixed effects of treatment, actual values of stratification factor at re-randomization, visit and treatment-by-visit interaction as covariates.

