- ITT_LT Population: Comparisons in Period B comparisons will be made between RZB/RZB and APR/APR based on the fixed term of treatment from a Mixed-effect Model Repeat Measurement (MMRM) model including the Baseline value and observed measurements at all post-baseline visits after Entry of Period B, adjusting for the fixed effects of treatment, actual values of stratification factor at Baseline, visit and treatment-by-visit interaction as covariates.

"Baseline" refers to the last non-missing observation on or before the date of the first administration of study drug, or the date of randomization if no study drug is administered.

"Entry of Period B" refers to the last non-missing observation on or before:

- The first dose date on or after re-randomization, or the date of re-randomization if no study drug is administered in Period B, for subjects who are randomized to APR at Baseline.
- The first dose date on or after Week 16, or the first visit date on or after Week 16 if no study drug is administered in Period B, for subjects who are randomized to RZB at Baseline.

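### Subjects rescued with risankizumab contribute no outcome to the Period B BSA comparisons, because the only scheduled BSA after Entry of Period B is at Week 52 and post-rescue values are dropped

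*SAP*

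**What the plan says.** SAP 3.3 lists change from Baseline in BSA among the other efficacy endpoints. SAP 9.5 states: "Additional efficacy endpoints will be compared between the APR/RZB and APR/APR treatment groups among the ITT_B_NR and ITT_B_Combined Populations". The same section adds RZB/RZB against APR/APR in ITT_LT.

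For continuous endpoints in ITT_B_NR, SAP 9.1 fits an MMRM that conditions on each subject's Baseline measurement. Its outcomes are "observed measurements at all post-baseline visits after Entry of Period B, adjusting for the fixed effects of treatment, visit and treatment-by-visit interaction as covariates". The ITT_B_Combined and ITT_LT models use the same visits and add stratification factors. For subjects who started on apremilast, the entry value is the last one up to "The first dose date on or after re-randomization, or the date of re-randomization if no study drug is administered in Period B".

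SAP 9.2.2 says that MMRM "will be the primary and only approach to handle missing data for continuous endpoints" in every ITT population except ITT_Res. Observations after alternative psoriasis treatment "or after the use of RZB as the rescue medication will be excluded from the model".

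On rescue, SAP 2.3 says: "Rescue risankizumab will be offered to subjects who are re-randomized to apremilast (Arm 2b) and are PASI 50 non-responders at Week 28", or at Week 40.

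In the Study Activities Table (Protocol Appendix D), BSA is ticked at Screening, Baseline, Week 16 and the shared Week 52/Premature Discontinuation column, and nowhere else. The sPGA/PASI row is ticked at every visit from Screening to Week 52.

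**The concern.** An MMRM copes with values removed after rescue because the subject's earlier values stay in the model and carry information about the missing ones. SAP 9.2.2 relies on this when it describes subjects with missing data at some but not all post-baseline visits. For BSA in Period B there are no earlier values to keep. A rescued subject is missing at every modelled visit and drops out of the likelihood.

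The loss is not random. Rescue is open only to APR/APR subjects below PASI 50, so the subjects removed are poor responders and all come from one arm. The SAP will report a treatment difference, 95% CI and p-value from what remains, labelled as an ITT comparison. The apremilast mean change will look better than it would have been without rescue, and the estimated benefit of switching will be too small.

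**Working it through.** **1. The plan's own figure.** The nearest stated figure is the power for Period B PASI 90: 50% against 20%, 60 per group, stated as more than 90%. The pooled proportion is 0.35. The null SE is √(2×0.35×0.65/60) = 0.0871, and the alternative SE is √((0.25+0.16)/60) = 0.0827. Power = Φ[(0.30 − 1.96×0.0871)/0.0827] = 94.1%, so it reproduces. It does not concern BSA, for which no size or power is stated.

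**2. Visits that enter the model.** After Entry of Period B, PASI has six scheduled visits (Weeks 20, 28, 32, 40, 44, 52). BSA has one (Week 52/PD). The Week 16 BSA is the entry value, not an outcome. ppIGA, NAPSI and PSSI have a Week 28 value, and DLQI, PSS and WPAI are collected at every visit. Among the additional continuous endpoints collected in Period B, only BSA has no value between entry and rescue.

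**3. Consequence.** A Week 52 or PD value in a rescued subject comes after rescue and is excluded. One remaining visit makes the MMRM an ANCOVA on Baseline in subjects with an observed value. Missingness depends on PASI at Week 28 or 40, which is not in that model, so missing at random given the modelled variables does not hold.

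**4. Direction and size in SD units.** Let a share r of APR/APR be eligible (the worst on the PASI selector), let a share u of these accept at random, and let ρ be the correlation of the selector with Week 52 BSA. The observed mean shifts towards better by ρ × u·φ(z_r)/(1 − r·u). With r = 0.4, u = 1, ρ = 0.6: φ = 0.386, and 0.6×0.386/0.6 = 0.39 SD. With u = 0.7: 0.6×0.7×0.386/0.72 = 0.23 SD. Over r = 0.2-0.6, u = 0.7-1 and ρ = 0.4-0.8, the shift is 0.09 to 0.77 SD, always in apremilast's favour.

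**5. Size in BSA points (ITT_B_NR, simulated).** All of these inputs are assumptions except the entry range:
- Baseline BSA is uniform on 10-15% (the entry criterion).
- PASI percentage improvement at Weeks 16, 28, 40 and 52 is exchangeable normal, capped at 100, with Week 16 below 75.
- A subject is eligible for rescue if Week 28 or Week 40 is below 50.
- BSA improvement has the same mean and SD as PASI improvement.
- APR/RZB improves by 85%, that is 12.5×0.85 = 10.63 points.

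Worked case (mean 55, SD 27, between-visit correlation 0.6, full uptake, PASI-BSA correlation 0.9): the mean APR/APR change is −6.13 in all subjects and −7.83 in those kept. The difference falls from −10.63 + 6.13 = −4.50 to −10.63 + 7.83 = −2.80, a shrinkage of 1 − 2.80/4.50 = 38%.

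Shrinkage by uptake and PASI-BSA correlation:

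| Apremilast PASI: mean / SD / correlation | Eligible | 70%, 0.6 | 70%, 0.9 | 100%, 0.6 | 100%, 0.9 |
|---|---|---|---|---|---|
| 45 / 25 / 0.5 | 79% | 8% | 11% | 23% | 34% |
| 55 / 27 / 0.6 | 68% | 11% | 16% | 26% | 38% |
| 65 / 30 / 0.7 | 60% | 15% | 20% | 30% | 42% |
| 85 / 27 / 0.5 (calibrated) | 32% | 16% | 19% | 25% | 31% |

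In the calibrated row about 19% of APR/APR reach PASI 90 at Week 52 without meeting rescue criteria, close to the 20% in SAP 2.4. In the first three rows the rate is 6% or less. ITT_B_Combined and ITT_LT were not simulated. They include PASI 75 responders, but the mechanism and its direction are the same.

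**The case against.** **Low decision weight.** Change in BSA is one of 18 other endpoints and lies outside both testing hierarchies. The primary and ranked Period B endpoints count rescued subjects as non-responders, and PASI change is modelled with the value that triggered rescue. The bias cannot create a false risankizumab advantage. All of this stands, and it limits the importance of the point. A reader might infer that the primary Period B result is in doubt; the documents do not support that.

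**Who remains.** A reader might infer that only the better apremilast responders are left. That goes too far. Rescue is offered, and exclusion follows use of rescue, not eligibility. Subjects below PASI 50 who decline keep their Week 52 BSA, and those who stop early without rescue may have a PD value.

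**Size.** Assuming full uptake, a PASI-BSA correlation of about 0.9 and low apremilast response, one can obtain 53-79% of the arm lost and 30-46% shrinkage. The documents support neither as an expectation, and those response rates sit far below the planned 20%.

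**Week 16 BSA.** SAP 9.2.2 also speaks of observed measurements at all visits, so Week 16 BSA might be admitted. That helps but does not cure. In an illustration with 40% rescued (selector correlated 0.7 with Week 52 BSA; Week 16 BSA correlated 0.6 with both), the bias falls from 0.45 to 0.27 SD.

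**Imputation.** Using PASI does not guarantee missing at random. At full uptake no off-rescue Week 52 BSA exists below PASI 50, so the model extrapolates. A one-step imputation still left up to about 0.4 point of bias.

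**Estimand.** The SAP defines none for additional endpoints. Dropping post-rescue data nevertheless implies the no-rescue quantity that the MMRM targets for the other continuous endpoints. The ITT_Res summary does not fill the gap, because it describes BSA after risankizumab.

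**Conclusion.** The concern holds as a defect in one additional endpoint. Read together, the activity schedule, SAP 9.1 and SAP 9.2.2 leave every APR/APR subject who receives rescue without a BSA outcome in ITT_B_NR, ITT_B_Combined and ITT_LT. The comparison is a complete-case one, selected on poor response in one arm, and is biased towards apremilast.

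The mechanism and direction follow from the documents. The size rests on assumptions, since no BSA mean, SD, rescue rate or PASI-BSA correlation is given. With uptake of 70-100% and correlation of 0.6-0.9, shrinkage is roughly 8-42%. With apremilast response calibrated to the planned 20% PASI 90 rate it is about 15-32%, reaching about 36% in the most adverse corner (SD 30, full uptake, correlation 0.9). Lower uptake reduces the bias without changing its direction. The sponsor should correct it, but no primary or ranked conclusion depends on it.

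**What to change.** In SAP 9.2.2, add a rule for Period B BSA in the three populations:

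- Replace the MMRM with sequential multiple imputation of the excluded post-rescue Week 52 BSA. Use Baseline and Week 16 BSA and all pre-rescue PASI values as predictors, and impute post-rescue PASI at later visits in order before imputing BSA.
- State that the target is the no-rescue quantity implied by the MMRM for the other continuous endpoints.
- Report the complete-case result as a sensitivity analysis, with the number of rescued subjects excluded per arm.
- Optionally, record BSA at Weeks 28 and 40 before any rescue dose, when the assessor already scores PASI.

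**Cost.** The main change needs SAP wording and programming on data already collected; SAP Appendix D already sets out the PROC MI steps. The interval will be wider. With high uptake the imputation extrapolates below PASI 50, and the report should say so. Appendix D justifies K=30 for under 30% missing information, so K should be raised if missingness exceeds 30%. The optional assessments need a change to the activity schedule.
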